#### IV. QUALITY ASSURANCE

1. Procedures in place to ensure the validity and integrity of the data: A modified version of a training manual developed for an earlier acceptability study of TTIP-PRO will be utilized. Two important elements missing from the acceptability study, which will be established for the present project, are: 1) training files and 2) an assessment of inter-rater reliability for the competence measure. The training files will include 4 mock interventions (1 video, 3 audio) and 4 audio recorded interventions with patient volunteers. Two TTIP-PRO trainers will rate two training files. Inter-rater reliability will be measured by intraclass correlation coefficients

(ICCs). If the ICC is less than .75 then clarifications will be made to the competence assessment and the trainers will rate two additional training files. This process will be repeated until an ICC greater than .75 is achieved. All TTIP-PRO sessions will be rated for providing fidelity and adherence by one of the two TTIP-PRO trainers. Potential Peer Interventionists will need to complete training and certification prior to being assigned participants.

2. Procedures to guarantee the accuracy and completeness of the data during data collection, entry, transmission and analysis: Assessments programmed in REDCap will use validation rules, integrity checks, and hard stops as needed to ensure that data are as complete and accurate as possible. The RA will check any data collected by paper source for completeness. As previously described, all data entered from a paper source will be double-entered and checked for consistency by REDCap.

## V. REGULATORY ISSUES

1. Reporting of AEs/ SAEs to the IRB, NIDA, and the FDA: All SAEs will be reported to the IRB and NIDA within 72 hours of their discovery. This is a behavioral study and so FDA reporting is not required. We will use FDA criteria for SAEs (i.e., an adverse event that results in any of the following outcomes; death, life threatening, requires hospitalization, initial or prolonged, results in disability, congenital anomaly, requires intervention to prevent permanent impairment or damage, or other significant medical event); OOD will be treated as an SAE. [name] or the designated study physician will assess the severity, relatedness, and outcome of each AE and SAE. It will also be Drs. [name]', [name]'s, and [name]'s responsibility to manage all AEs and SAEs and to make referrals for appropriate care, as necessary. All participant information will be de-identified when reporting SAEs. All AEs and SAEs will be reported to and reviewed by the DSMB at the time of their standard meeting, except when [name] or the designated study physician thinks that the SAE is very severe and/or may require a protocol amendment. In that case, [name] may request an ad hoc review by the DSMB. All AEs and SAEs will be entered into a database that is de-identified and password protected to ensure confidentiality.
2. Reporting of IRB action to NIDA: All communications with and actions of the IRB will be kept in a regulatory binder specific for this study. Any protocol changes, amendments, or deviations will be submitted to the IRB and NIDA and the IRB's actions will then be reported to NIDA. Any other IRB actions (including annual re-approvals and correspondence related to DSMB reports) will be submitted to NIDA.
3. Report of changes or amendments to the protocol: All changes and amendments to the protocol will be submitted to the IRB and NIDA. Only after IRB and NIDA approvals are granted will the changes and amendments be implemented.
4. Trial stopping rules: Individual study participants will be informed of their right to discontinue study participation at any time during the study. The PI/Medical Monitor may discontinue a participant or Peer Interventionist's trial participation if deemed clinically appropriate. The DSMB may recommend study termination based on review of site performance or safety and efficacy data. NIDA has the right to discontinue the investigation at any time.
5. Disclosure of conflict of interest: The investigators and members of the data safety and monitoring board (DSMB) have no conflicts of interest.

## VI. TRIAL SAFETY

1. Potential risks and benefits for participants: This project includes two types of participants: 1) the participants who may receive the TTIP-PRO intervention, referred to as participants, and 2) the participants who will serve as Peer Interventionists.

**Risks associated with the TTIP-PRO intervention.** TTIP-PRO consists of two parts: 1) an information packet which includes three reports (“Personal Overdose Risk Factors Report”; “Medication Assisted Treatment (MAT) Report”; and the “Opioid Overdose Information Report”) generated from the participant’s responses to two surveys and information about how to access treatment at a UC ASD (UC Health/UCPC) MAT program; 2) a 20-minute telephone intervention delivered by Peer Interventionists. The Peer Interventionists interact with the study participants only on the phone, not in person, and, thus, physical safety is not a concern. The phone intervention may last up to 20 minutes during which the Peer Interventionist will answer the participant’s questions about the information packet reports, with the potential answers being highly scripted, and an exchange of information between the Peer Interventionist and participant about MAT.

Potential risks of TTIP-PRO for participants include: 1) breach of confidentiality and 2) improper administration of the intervention by the Peer Interventionist. The Peer Interventionists will be provided with the first name and phone number of the participants assigned to them in a secure manner. As part of their training, the Peer Interventionists will be instructed on methods for maintaining confidentiality. Several steps will be taken to ensure proper administration of the intervention. First, all Peer Interventionists must complete a 4-hour training and certification before being assigned study participants. For certification, a TTIP-PRO trainer will rate the trainee’s performance on a mock intervention. The trainer will use a 3-point scale (1-Meets expectations, 2-Needs improvement, 3-Expectations not met and additional training required). To be certified, the trainee needs to receive a “1” on at least 5 of the 6 abilities assessed: 1) Ability to provide information while maintaining a conversational tone; 2) Ability to successfully complete the intervention within 20 minutes; 3) Ability to listen; 4) Sufficient familiarity with correct information about OOD and MAT to answer the participant’s questions; 5) Ability to remain non-judgmental and encouraging; and 6) Ability to avoid confrontation. Second, all interventions will be audio recorded and rated for adherence/fidelity using the same assessment as that used for certification. Any instance of falling below certification criteria will result in additional training or discontinuation from the trial depending on the nature of the problematic performance.

Potential risks of TTIP-PRO for Peer Interventionists include: 1) breach of confidentiality and 2) increased risk of relapse. In order to diminish the possibility of the participants discovering PHI about the Peer Interventionists, a study cell phone, rather than the Peer Interventionist’s personal cell phone will be used; this will avoid the potential for the participant obtaining the Peer Interventionist’s phone number and then using the number to determine information about the Peer Interventionist (i.e., name, address). The Peer Interventionists will be exposed to active users during the 20 minute telephone intervention. As noted above, for individuals early in recovery or struggling with recovery and/or other issues, interacting with active users could increase the risk of relapse. Our Peer Interventionist eligibility criteria are designed to select only those individuals whose recovery is sufficiently stable to mitigate this risk. The consent form will clearly delineate relapse as a potential risk. The potential Peer Interventionist will need to agree to an ongoing exchange of information between the research team and his/her treatment providers in order to monitor his/her clinical status. [name] and her research team are co-located with the clinic staff for the UC ASD MAT program and interact on a daily basis; the clinic staff will be instructed to inform the research team of any deterioration in the Peer Interventionist’s functioning. In the event of clinical deterioration, the clinic’s multi-disciplinary team will develop a treatment plan, which may include the Peer Interventionist’s discontinuation from study participation. Peer Interventionists will be compensated \$40 for completing training/certification, and \$20 for each participant for whom they provide the intervention. Peer Interventionists will not be compensated with cash, which could potentially be used to purchase illicit opioids but, rather, with a prepaid debit card.

**Risks associated with study participation.** Breach of confidentiality: As with any study, there is a potential risk of loss of confidentiality. To maintain confidentiality, study records and data will be stored in compliance with the International Conference on Harmonization (ICH) guidelines. Participant/Peer Interventionist records will be held confidential by the use of study codes in the study database, secure storage of any documents that have participant identifiers, and secure computing procedures for entering and transferring electronic data. No

identifying information will be disclosed in reports, publications or presentations. Information collected for this study will be kept in a locked secure location accessible only to research staff and authorized personnel directly involved with this study. Finally, a Certificate of Confidentiality will be obtained for the study. Emotional Discomfort: The participants may experience some emotional discomfort from answering sensitive and/or personal questions. Participants may experience embarrassment in answering questions about their knowledge of MAT and OOD. The participants/Peer Interventionists can choose to not answer questions that they find to be too uncomfortable and will be reminded that study participation is completely voluntary. NARCAN® Nasal Spray kit. This medication has a very favorable side-effects profile. However, there have been rare cases in which using naloxone to reverse an OOD has resulted in vomiting, sweating, shaking, tachycardia, elevated blood pressure, seizures, pulmonary edema, ventricular dysrhythmias, rapid pulmonary edema, and cardiac arrest.

**Benefits.** The results of the present pilot study are unlikely to have a direct substantial societal impact. However, promising pilot results would be used in support of a larger trial to test the efficacy of the TTIP-PRO in reducing the recurrence of opioid overdoses. Should that project yield promising results, the benefits to individuals and to society could be substantial. Both the study participants and the Peer Interventionists may directly benefit from study participation in that they will receive information about risks for overdose, the signs of overdose, how to respond to an overdose, and factors that can reduce the risk of an overdose. The study participants may also benefit from receiving a NARCAN® Nasal Spray kit. Consequently, the risk/benefit ratio is favorable and conduct of the research well justified.

2. Collection and reporting of AEs and SAEs: In general, the risks associated with trials employing behavioral interventions are presumed minimal relative to those evaluating pharmacologic interventions. Based on the TTIP-PRO acceptability study the risk from TTIP-PRO is low. Still, for the present trial, the population studied is a vulnerable population and possibly at higher risk given the nature of the disorder and the population. Thus, the following events, which are not defined as SAEs, will be tracked on an AE CRF for participants and Peer Interventionists:

1. Suicidal ideation
2. Homicidal ideation

In addition, the following events will be track on an AE CRF for the Peer Interventionists:

1. Discharge from MAT program for any reason
2. Illicit opioid use
3. Other clinical deterioration as reported by clinic staff

For TTIP-PRO, which is a behavioral trial, the RA is primarily responsible for assessing the occurrence of AEs/SAEs with oversight by the Study Medical Monitor and PI. For Participants, the RA will query about how s/he has been feeling since the last visit (i.e., at the follow-up phone call in week 3 and in-person visits at 3, 6-, and 12-months following enrollment). For Peer Interventionists, the RA will query about how s/he has been feeling following the delivery of each TTIP-PRO intervention. All AEs/SAEs occurring during the course of the clinical trial will be collected, documented, and reported by the investigator or sub-investigators in accordance with reporting requirements. [name] or the designated study physician will assess the severity, causality and outcome of all AEs and SAEs. It will also be Drs. [name]', [name]'s, and [name]'s responsibility to manage all AEs and SAEs and to make referrals for appropriate care, as necessary. All SAEs will be reported to the University of Cincinnati Institutional Review Board and the NIDA project officer within 72 hours of their discovery. All subject information will be de-identified when reporting serious adverse events.

3. Management of SAEs or other study risks: Please refer to Section VI. 1. for management of study risks.

## VII. TRIAL EFFICACY

1. Plans for interim analysis of efficacy data: There will be no interim analysis of efficacy data by the investigators. However, the DSMB (see below, Section IX, 5) will monitor efficacy data and provide recommendations regarding whether the study should continue without modification or with modification or be terminated.

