## **E. METHODS**

### **1.0 Study Design**

#### **1.1 Overview of study design**

Following finalization of the Peer Interventionist training materials (described below in section 3.0), a pilot efficacy trial will be completed. This pilot study is a randomized controlled intent-to-treat (ITT) clinical trial. Potential participants will be recruited through various methods, which include but are not limited to advertisements, flyers, and word-of-mouth. Approximately eighty eligible participants will be randomized in a 1:1 ratio to the control condition (Information and NARCAN® Nasal Spray kit) or to the experimental condition (TTIP-PRO in addition to the elements provided in the control condition). All participants will complete a follow-up phone call approximately 3-weeks post-randomization, during which process measures will be completed, and in-person visits at approximately 3, 6-, and 12-months following enrollment.

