### 5.2 Data Analysis

All analyses will be completed on the ITT sample using SAS (SAS Institute, Inc.). Statistical tests will be conducted at a 5% Type I error rate (two-sided) for all measures. It has been recommended that effect sizes be provided rather than using the Bonferroni procedure to adjust for multiple-comparisons; thus, effect sizes and 95% confidence intervals (CI's) will be computed for each treatment effect. For each efficacy analysis, demographic/baseline characteristics and length of time since last OOD will be selected for inclusion in the model using the corrected Akaike Information Criterion (AICC) as the optimizing criterion. For missing data, multiple imputation methods will be used and the resulting model compared to the non-imputed model. **Participant Analyses**-The primary hypothesis, that a significantly greater proportion of TTIP-PRO, relative to control, participants will enter MAT within 12-month follow-up will be tested using a logistic regression (a generalized linear model with a logistic link). Secondary analyses. The key secondary hypothesis, that a significantly lower proportion of TTIP-PRO, relative to control, participants will have a recurring OOD within 12-month follow-up will be tested using a logistic regression (a generalized linear model with a logistic link). The secondary hypothesis that TTIP-PRO, relative to control, participants will have a significantly greater reduction in illicit opioid use will be tested using two outcomes, one based on self-report and the other on UDS results. The proportion of self-reported use days will be treated as a binomial variable and regressed using logistic mixed model regression (random-intercept generalized mixed-model regression with a logistic link function). UDS results (positive for illicit opioids vs. not positive), will be treated as a binary variable which will also be regressed using logistic mixed-model regression. For both outcomes, the effects of interest will be treatment and treatment-by-time interaction.

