#### VIII. DSM PLAN ADMINISTRATION

1. Responsibility for data and safety monitoring: Drs. [name], [name], and [name] will be responsible for the clinical management and safety monitoring of the study participants and Peer Interventionists.
2. Frequency of DSM reviews: The study protocol will be reviewed by the DSMB before recruitment starts. Efficacy and AE/SAE data will be reviewed by the DSMB every six months for the duration of the trial. The DSMB reports will be submitted to the IRB and NIDA. Additionally, annual reports will be sent to the IRB for re-approval of the study. SAEs will be reported and reviewed by the DSMB at the time of their meeting, except when [name] or the designated study physician thinks that the SAE is very severe and/or may require a protocol amendment. In that case, [name] may request an ad hoc review by the DSMB. Each SAE will be reported in writing at the time of occurrence (within 72 hours) to the IRB and NIDA.
3. Content of DSM report: The DSM report will include a brief description of the trial and any changes made to the trial. Additionally, we will report baseline sociodemographic characteristics, including age, gender, and race of the subjects screened and randomized. We will also report retention rates and the disposition for all study participants and Peer Interventionists. Finally, any quality assurance issues, regulatory issues, AEs and SAEs will be included in the report. After review of the data, the DSM report will make recommendations about whether the trial should continue with or without modifications or be terminated.

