#### IX. DSM BOARD (DSMB) PLAN

1. Members and affiliation: Members for the DSMB will include: 1. [name], Professor, University of Cincinnati College of Medicine, who has extensive expertise in data analysis for clinical trials. 2. [name], MBA who is an emergency medicine physician at the University of Cincinnati Medical Center. 3. [name], staff Psychiatrist at the Cincinnati Veterans Medical Center, who is board certified in both Internal Medicine and Addiction Medicine.
2. Frequency of meetings: The DSMB will meet before recruitment starts, and then every six months. The PI may request an ad hoc review more frequently if protocol amendments are needed.
3. Conflict of interest: The DSMB members report no conflicts.
4. Protection of confidentiality: All participant data will be de-identified prior to review by the DSMB to maintain participant confidentiality. Only participant ID number, gender, age, and race will be provided to the DSMB.
5. Monitoring activities (initial and ongoing study review): The DSMB will review the protocol prior to participant enrollment and will provide recommendations for any protocol changes in order to maximize safety or efficacy assessments. The DSMB will then formally meet before recruitment starts, then at a minimum of every 6 months during the course of the study. The DSMB will review the disposition of all study participants and reasons for study drop-out. The DSMB will also review all SAEs. [name], the project statistician, will be responsible for providing updated safety data to the DSMB prior to each meeting. The DSMB will provide a written report of their recommendation as to whether the study should continue, be modified, or should be terminated.
6. Communication plan to IRB and NIDA: [name], in conjunction with the DSMB, will be responsible for making certain that the DSMB files their report to the IRB as well as to the sponsor (NIDA) of the study.

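### The DSMB may recommend termination on six-monthly efficacy data with no boundary, so the 5% level is not protected, and the DSMP conflicts on whether the board receives such data

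*Combined protocol and SAP*

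**What the plan says.** Three parts of Appendix B (the DSMP) give the DSMB an efficacy role.

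- VIII.2: "Efficacy and AE/SAE data will be reviewed by the DSMB every six months for the duration of the trial".
- VII.1: the board "will monitor efficacy data and provide recommendations regarding whether the study should continue without modification or with modification or be terminated". The sentence before it excludes interim efficacy analysis, but only by the investigators.
- V.4, headed as the trial stopping rules: "The DSMB may recommend study termination based on review of site performance or safety and efficacy data".

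None of these gives a threshold, a spending rule or a futility rule, or says that the trial will not be stopped for benefit.

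The final analysis takes no account of the reviews. Section 5.2 states: "Statistical tests will be conducted at a 5% Type I error rate (two-sided) for all measures". DSMP III.3 repeats this. The only text on multiplicity prefers that "effect sizes be provided rather than using the Bonferroni procedure to adjust for multiple-comparisons", which concerns several outcomes and not several looks.

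Other DSMP parts describe a board without efficacy data. VIII.3 lists no efficacy content in the report. IX.5 says that the statistician "will be responsible for providing updated safety data to the DSMB prior to each meeting". IX.4 says: "Only participant ID number, gender, age, and race will be provided to the DSMB".

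**The concern.** A 5% test is a 5% test only if nothing in the conduct of the trial gives the result extra chances to be declared positive. Here a board may look at efficacy several times and recommend termination or modification on what it sees, and nothing limits how it may do so. If it reacted to an early favourable difference at the usual threshold, the chance of a false positive on MAT entry could exceed 5%. The effect estimate passed to the full-scale trial would tend to be too large, and later enrollees could lose part of the 12-month follow-up that defines the primary outcome.

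Separately, the DSMP does not tell the statistician what to send. One set of sections requires efficacy review; another supplies nothing to review.

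**Working it through.** **1. The plan's own figure.** Inputs: "Approximately eighty eligible participants will be randomized in a 1:1 ratio" (section 1.1), so 40 per arm; 12% v 39% MAT entry and two-sided .05 (section 5.2, Power).

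- Mean rate (.12 + .39)/2 = .255.
- Null SE = √(.255 × .745 × 2/40) = .0975.
- Alternative SE = √(.12 × .88/40 + .39 × .61/40) = .0927.
- Power = Φ[(.27 − 1.96 × .0975)/.0927] = Φ(.85) = 80.3%.

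The stated 80% reproduces. It spends the whole .05 on one final test.

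**2. Number of looks (assumption).** Section 6.0 gives about 14 months of enrolment and 12 months of participation, so 26 months in all. Six-monthly reviews then fall near months 6, 12, 18 and 24, plus a final analysis. The documents do not fix this number: IX.5 makes six months a minimum frequency and ad hoc reviews are allowed.

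**3. Normal theory.** The statistics at information fractions t₁<t₂ have correlation √(t₁/t₂), and the error is P(any |Z|>1.96) under no effect.

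| Rule applied | Overall error |
|---|---|
| Test at .05, stop in either direction; 2, 3, 4, 5 equally spaced analyses | 8.3%, 10.7%, 12.6%, 14.2% |
| Same, 12-month completers only, months 18, 24, 26: t = 6/14, 12/14, 1 | 9.8% |
| Early stop for benefit only; 3, 4, 5 analyses | 7.9%, 8.8%, 9.6% |
| Early stop only when the effect is below zero (futility); 3 to 5 analyses | 2.2% to 2.4% |
| p<.001 at interims, .05 at the end; 3 to 5 analyses | about 5.1% |

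**4. At the trial's own size.** Simulation of 80 participants: uniform 14-month accrual, a constant rate of MAT entry, no true effect, looks at months 6, 12, 18, 24 and final, p<.05 at any look. The 12% rate is the plan's control rate; 25% is an assumption to show the range.

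| Test | 12% in both arms | 25% in both arms |
|---|---|---|
| Pooled z | 11.1% | 12.8% |
| Likelihood ratio | 16.2% | 16.1% |
| Wald (zero cells counted as non-significant) | 2.5% | 7.7% |

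For the pooled z test, the final analysis alone gives 5.7% and 4.9%. If early stops are for benefit only, the z and likelihood-ratio tests give about 8-11%. With 20,000 trials the Monte Carlo standard error near 11% is √(.11 × .89/20,000) = 0.2 percentage points. Section 5.2 names logistic regression but not the form of the test, and the AICC-selected covariates are not simulated here.

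With p<.001 at the interim looks, the final error is essentially unchanged under all three tests.

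**5. Data supply, side by side.**

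| DSMP section | What it implies |
|---|---|
| V.4, VII.1, VIII.2 | The board sees efficacy data and may act on them |
| VIII.3 | The report holds characteristics, retention, disposition, quality and regulatory issues, AEs and SAEs; no efficacy |
| IX.5 (the section that VII.1 cites) | Safety data, disposition, drop-out and SAEs |
| IX.4, read literally | ID, gender, age and race only |

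These cannot all be followed.

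**The case against.** A reader might infer that the 5% level is broken, or that the plan contradicts its own error rate. The documents do not support this. Inflation needs a rule that stops or changes the trial for apparent benefit at an unadjusted threshold, and no section contains one. A reference to efficacy data also covers futility and harm. Looking without acting costs nothing, and futility stopping lowers the error. If VIII.3 and IX.5 govern, the board sees no efficacy data and there is no inflation at all.

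A reader might also infer that VII.1 denies an interim analysis and then describes one. It does not: the denial covers the investigators, and the next sentence gives the task to the board.

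Nor is a doubled error rate a safe summary. At the plan's 12% rate a Wald test stays below 5% even with five unadjusted looks. The early looks are also thin: at month 6 about 80 × 3/14 = 17 participants have passed a three-month visit, with fewer than one MAT entry expected.

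Finally, IX.4 sits under a confidentiality heading. Read literally it would bar the SAE and disposition data that IX.5 supplies, so it was probably meant for identifying or demographic fields. And section 5.2 calls the pilot more useful for feasibility than for estimating an effect; the board only recommends.

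All of this limits the size of the problem. It does not supply the missing rule. The one section on stopping names efficacy without a criterion, the primary hypothesis is still tested at 5%, and the data-supply sections still disagree.

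**Conclusion.** The point stands as a lack of protection, not as a demonstrated excess. The true error rate cannot be computed, because the plan gives neither a decision rule nor a fixed number of looks. If the board stopped on an unadjusted p<.05, the error under the assumed five analyses would lie anywhere from 2.5% (Wald, 12% entry) to about 16% (likelihood ratio), with 11-13% for the pooled z test. The conflict over whether the board receives efficacy data needs no assumption. The weight is moderate: this is an 80-person pilot, but promising results are meant to support a larger trial, and the correction is cheap.

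**What to change.** - **V.4, VII.1, VIII.2:** make these agree. Preferably state that the DSMB will not recommend early stopping for apparent benefit. Harm review can remain, as can non-binding futility review if wanted; neither raises the chance of a false claim of benefit. The final .05 and the 80.3% power are then unchanged.
- **If stopping for benefit is kept:** require p<.001 (Haybittle-Peto) at every interim look and keep .05 for the final test. The overall error is about 5.1%. For comparison, O'Brien-Fleming boundaries with 3 to 5 analyses would put the final level at .045 to .041 and final-test power at 79.0% to 77.9%.
- **VIII.3 and IX.5:** name the by-arm outcome data that the statistician supplies in a closed report.
- **IX.4:** say that the limit applies to identifying or demographic fields.

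The cost is DSMP wording, with no added participants. The downside is that a stop for benefit becomes very unlikely, which matters little in a pilot of this size.
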